Exclusion criteria: absolute contraindication to phentermine or topiramate (i.e. phentermine: history of coronary artery disease, stroke, arrhythmia, congestive heart failure, uncontrolled hypertension), hypersensitivity to sympathomimetic amines, current or recent (within 14 days) use of monoamine oxidase inhibitors, glaucoma, or hyperthyroidism; topiramate: hypersensitivity to topiramate, history of nephrolithiasis), concomitant use of phenytoin, carbamazepine, or carbonic anhydrase inhibitors (e.g. zonisamide, acetazolamide, or dichlorphenamide), use of anti-obesity medication within 6 months of screening, initiation of a new medication associated with weight loss or gain within 30 days of screening, hypothalamic obesity, unmanaged (e.g. without medications and/or psychotherapy) clinically significant (determined by a mental health professional using diagnostic instruments and/or clinical interview) depression or anxiety, history of any suicidal behavior within 30 days of screening or any suicidal ideation with either some intent to act or with intent and a specific plan within 30 days of screening, history of severe psychiatric disorders (i.e. schizophrenia), severe hepatic impairment (ALT >10x upper limit of normal or known synthetic liver dysfunction), moderate or severe renal impairment (GFR <30mL/min/1.73m²), inability to meet minimum nutrition requirements, current pregnancy/plans to become pregnant for 16 weeks from study drug start date, and any females without a long acting reversible contraceptive (LARC) who do not commit to using 2 forms of birth control. (Of note, the vast majority of female patients undergoing surgery have a LARC placed intra-operatively, significantly reducing pregnancy risk during the trial). Patients on medications for hypertension, dyslipidemia, depression, and anxiety should be on these at a stable dose for >4 weeks prior to study enrollment, and on contraception for >7 days prior to study enrollment.

- Maximum number of subjects (patients + parent/guardian/LAR counted separately) needed to consent at all sites: 60
- Maximum number of local subjects (patients + parent/guardian/LAR counted separately) that will be consented, including screen failures and withdrawals: 60
- Number of local subjects (patients + parent/guardian/LAR counted separately) necessary to collect sufficient data to answer the research question: 20

Recruitment and Informed Consent/Assent Plan:

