The PI and/or professional research assistant (PRA) will review the charts of bariatric surgery patients prior to their projected Screening Visit (6, 9, or 12 months postoperatively) to assess the percent weight loss trajectory over the preceding postoperative visits to identify those who have not achieved expected weight loss and/or whose baseline BMI was so high that even if they were to achieve expected weight loss, they would continue to have severe obesity. Chart review for evidence of any exclusion criteria will also be performed. For patients who don't have any exclusion criteria by chart review and attend the postoperative clinical visit 3 months prior to their projected Screening Visit, the PI/PRA will present them the Recruitment Flyer either in person, via secure video call, via research MyChart message in the Epic electronic medical record, or by telephone with the Recruitment Flyer emailed. For those who express interest, the study team will at the same time complete the Pre-screening Consent Script requesting permission to contact the family within the week before their Screening Visit with a reminder to fast, if not already done clinically. On the day of the Screening Visit, the PI/PRA will review the measured weight/height to confirm whether or not weight/BMI inclusion criteria are met. If weight/BMI inclusion criteria are met, the PI/PRA will approach the individual and parent/guardian/LAR/proxy during that visit to discuss eligibility. complete the inclusion/exclusion criteria form, obtain consent/assent if the patient/parent qualify and are interested, and collect Enrollment Visit measures.

[figure not shown]

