the participant in advance of the informed assent discussion using REDCap's survey distribution tool. The eAssent form is designed to allow the participant to navigate forward and backward through the entire form and to access the form at a later time if desired. During the informed assent discussion, the potential participant's questions will be answered and at the end, the participant will verbally confirm they agree to be in the study. Because there can only be one signature ("certifier") for each REDCap eAssent form, there are separate REDCap eAonsent forms for the adolescent/young adult and the researcher presenting the form. The eAssent gives subjects the option to download a copy of the signed form. If a participant refuses or is unable to eAssent but is still interested in participating, a physical assent will be collected by the study team at the next inperson visit to the bariatric surgery center.

C. Study Design and Research Methods

Figure 1. Study Design

The pharmacotherapy group will receive oral phentermine and immediate release topiramate in combination, up-titrated to goal doses of 16mg and 100mg, respectively over 4 weeks*, then maintained at this dose for 8 additional weeks. Topiramate is gradually down-titrated during weeks 13 and 14 to prevent possible discontinuation symptoms.

Dosing Schedule^{†,§}

Uptitration:

- Week 1: 4mg phentermine + 25mg immediate release topiramate
- Week 2: 8mg phentermine + 50mg immediate release topiramate
- Week 3: 12mg phentermine + 75mg immediate release topiramate

Goal Dose:

- Weeks 4-12: 16mg phentermine + 100mg immediate release topiramate **Discontinuation (at study Visit 4)**:
- Week 13: Discontinue Phentermine + Decrease topiramate to 50mg
- Week 14: Decrease topiramate to 25mg for 7 days, then discontinue
- (*) Participants who do not tolerate goal doses will be maintained at the highest tolerated dose. (§) Per existing literature³⁴ and discussion with pharmacy, participants with moderate hepatic impairment (ALT >3x ULN but <10x ULN on two consecutive measures outside of acute illness, and no evidence of hepatic synthetic dysfunction), will follow the same dosing schedule, with doses reduced as needed

based on side effects (See Procedure for Study Drug Dose Reduction/Discontinuation).

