- 8) The Children's Colorado Bariatric Surgery Center is medically supervised by Drs. [name] (Nutrition), [name] (Endocrinology), [name] (Gastroenterology/Liver), and [name] (Cardiology). The behavioral health specialist within the Bariatric Surgery Center is pediatric clinical psychologist [name]. In the event of an adverse cardiovascular side effect associated with phentermine use as part of this study, we have the ability to obtain prompt clinical evaluation by a Lifestyle Medicine cardiologist. Similarly, in the event of an adverse side effect related to mood, we have the ability to arrange a prompt mental health evaluation with a Lifestyle Medicine clinical psychologist. The PI and primary mentor/bariatric clinic medical director [name] will manage any other physical medical side effects that may arise.

Phentermine Risk Mitigation Strategy (also see Table 2):

Steps to mitigate potential risks related to phentermine in this study include exclusion of individuals with any absolute contraindication to phentermine (as defined by the FDA label), drug interaction check prior to initiation, review of baseline kidney function, ALT, urine pregnancy tests at enrollment and every study visit, baseline echocardiogram per standard of care in individuals with hypertension or severe obstructive sleep apnea + known poor adherence to positive pressure therapy who have not had one in the previous 6 months, documented commitment from female participants who don't have a LARC, to use two forms of

birth control, phone calls at 1, 2, and 3 weeks after study pill initiation and weekly during any additional titration during the protocol to assess for adverse effects, and evaluation of heart rate, blood pressure, comprehensive review of systems and a physical exam performed by a study physician at enrollment and every study visit.

Topiramate

- 1) The present study proposes to use generic immediate release topiramate tablets.
- 2) Topiramate alone is not FDA-approved to treat obesity at any age.
- 3) In pediatrics, there is extensive experience using topiramate in children as young as 2 years old for seizure disorders with dosing frequently between 200-400mg/day, compared to the 100mg per day maximal dose proposed in this study. Topiramate is also FDA-approved for migraine prophylaxis in adolescents 12 years and older at a recommended dose of 100mg/day.

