- 4) Topiramate is a known teratogen. All female bariatric surgery candidates routinely undergo contraceptive counseling preoperatively with a gynecologist. The vast majority of females have a long acting reversible contraceptive (LARC) placed prior to or at the time of surgery.
- 5) Potential adverse effects of topiramate include paresthesias, fatigue, dysgeusia, psychomotor slowing, nephrolithiasis, anhidrosis/hypohidrosis, trouble with memory/concentration/word finding, and change in mood.⁴⁰ In the event of an adverse side effect related to mood, we have the ability to arrange a prompt mental health evaluation with clinical psychologist [name]. The PI and primary mentor/bariatric clinic medical director [name] will manage any physical medical side effects that may arise.

Topiramate Risk Mitigation Strategy (also see Table 2):

Although the weight loss effect of topiramate is dose-dependent up to ~200mg/day, ⁴¹ adverse cognitive side effects are more commonly seen at doses over 100mg/day, and also when topiramate is not gradually uptitrated. ^{42,43} Thus, the maximum dose chosen for this study is 100mg/day using a gradual up-titration of 25mg per week. Additional steps to mitigate potential risks related to topiramate include exclusion of individuals with any absolute contraindication to topiramate (as defined by the FDA label), drug interaction check prior to initiation, review of baseline bicarbonate, kidney function, ALT, documented commitment from female participants who don't have a LARC to use two forms of birth control, urine pregnancy test at enrollment and every study visit, phone call at 1, 2, and 3 weeks after study pill initiation and weekly during any additional titration during the protocol to assess for adverse effects, and comprehensive review of systems and a physical exam performed by a physician at enrollment and every study visit.

Phentermine + Topiramate

- 1) Extended release topiramate in combination with phentermine (trade name Qsymia) is FDA approved for chronic weight management in adults 18 years and older with a BMI ≥30kg/m2 or ≥27kg/m2 plus an obesity-related comorbidity.
- 2) Phentermine and Topiramate were paired to theoretically reduce/neutralize the side effects seen with either medication alone, and additively or synergistically impact weight loss.

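### The renal exclusion names moderate and severe impairment, but its only bound, GFR below 30, reaches only the severe grade under usual grading (an assumption)

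*Combined protocol and SAP*

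**What the plan says.** Section IV.B (Description of Population to be Enrolled), in the exclusion criteria, lists "moderate or severe renal impairment (GFR <30mL/min/1.73m²"). No other GFR value or renal grading appears in the document.

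The same sentence sets the hepatic criterion, which names only the severe grade: "severe hepatic impairment (ALT >10x upper limit of normal or known synthetic liver dysfunction"). The § footnote to the dosing schedule in Section IV.C then deals with the next grade down, "participants with moderate hepatic impairment (ALT >3x ULN but <10x ULN on two consecutive measures outside of acute illness", and no evidence of synthetic dysfunction. Those patients stay in the trial and "will follow the same dosing schedule, with doses reduced as needed" for side effects.

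Kidney function is also mentioned in the two risk mitigation strategies in Section IV.D.1. For phentermine the text is "review of baseline kidney function, ALT, urine pregnancy tests at enrollment and every study visit"; for topiramate it is "review of baseline bicarbonate, kidney function, ALT". Table 3 schedules a basic metabolic panel at screening/enrollment and at Visits 2 and 4. None of these places gives a GFR cut-off.

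On who applies the criteria, the recruitment plan in Section IV.B says "Chart review for evidence of any exclusion criteria will also be performed". At the screening visit the investigator or research assistant is to "complete the inclusion/exclusion criteria form".

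**The concern.** The line states its rule twice, once in words and once as a number, and on the usual meaning of the words the two do not agree. Following the number admits a grade that the same line names as excluded. Following the words leaves the screener without a cut-off for moderate.

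This is a safety criterion in a placebo-controlled drug trial that includes minors. The plan itself treats renal risk as real: a history of nephrolithiasis is an exclusion, and Table 2 lists kidney stones and metabolic acidosis among the rare but serious topiramate risks. A patient with moderate renal impairment who was let in by the number would follow the standard titration to 16 mg phentermine and 100 mg topiramate, because the dosing schedule has a footnote for moderate hepatic impairment and none for renal impairment. Two people screening the same patient, one by the words and one by the number, could also reach different decisions.

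**Working it through.** No figure in the plan can be recomputed here. The check sets the wording against its bound and then looks for anything elsewhere that settles the difference.

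**Step 1. The bound.** The plan's renal threshold is GFR below 30 mL/min/1.73m² (Section IV.B). The risk mitigation strategies, Table 2, Table 3 and the drug discontinuation criteria (Section IV.D, Data and Safety Monitoring Plan, item 6) contain no second threshold and no definition of renal grades.

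**Step 2. The grading (assumption, not in the documents).** Severe is below 30. Moderate runs from 30 to an upper limit of 44, 49 or 59, depending on the scheme.

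| Assumed moderate band | Excluded by the words | Excluded by the number | Range in conflict |
|---|---|---|---|
| 30-44 | up to 44 | below 30 | 30-44 |
| 30-49 | up to 49 | below 30 | 30-49 |
| 30-59 | up to 59 | below 30 | 30-59 |

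A GFR of 40 lies in the moderate band in all three rows and is not below 30, so the words exclude the patient and the number admits the patient every time. The upper limit changes only the width of the conflict. Its existence depends on moderate starting at 30. It disappears only under a grading that puts the whole of moderate below 30, and the documents cite none.

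**Step 3. The hepatic comparison.**

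| Organ | Severe | Moderate |
|---|---|---|
| Liver | Excluded, ALT >10x ULN or known synthetic dysfunction | Own band, ALT >3x to <10x ULN; kept in, with a dosing footnote |
| Kidney | Excluded | Named as excluded; no band of its own and no dosing footnote |

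For the liver the plan separates the grades and gives each its own number. For the kidney it joins them under one number. That the renal line goes out of its way to name moderate, where the hepatic line does not, leans towards an intent to exclude it. It does not prove that intent.

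**Step 4. Exposure.** Randomisation is 1:1 with 7 of 14 per arm, so any such patient admitted has a 7/14 = 50% chance of active drug. The documents do not say how many clinic patients have a GFR in the conflict range.

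**Step 5. Recruitment cost of a higher bound.** Section III expects 14 eligible patients against a target of 10 and describes the gap as a 29% allowance for decline and dropout. That reproduces: (14 − 10)/14 = 28.6%. New ineligibility is not part of the allowance, so each patient lost to a higher bound reduces it. With 0 to 2 lost (an assumption):

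- 0 lost: 4/14 = 28.6%
- 1 lost: (13 − 10)/13 = 3/13 = 23.1%
- 2 lost: (12 − 10)/12 = 2/12 = 16.7%

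**The case against.** The strongest reply is that the parenthesis is the definition. The hepatic criterion in the same sentence is built the same way, a grade followed by its numeric test. Read so, the renal line has one usable rule, GFR below 30, and the problem is at most a redundant word. This reading does make the line workable. But under the assumed grading the reference to moderate then excludes nobody, and anyone reading the words would credit the trial with a protection it does not give.

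A second reply is that the conflict itself, not merely its size, comes from an outside convention. That is correct, and the conclusion is conditional on it.

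Third, screener disagreement is speculative: this is one centre, the research assistant reports to the principal investigator, and the eligibility form is not in the documents, so it may already carry a clear rule. That stands; disagreement is possible but not shown.

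Fourth, since intent is unknown, preferring the higher bound takes a side. The hepatic comparison is weak evidence, and a request for clarification could be thought enough. Against that, on a safety criterion the more protective reading is the sound default until the sponsor confirms otherwise, and its cost is small.

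Existing safeguards also limit harm: baseline kidney function is reviewed for both drugs, the metabolic panel is repeated at Visits 2 and 4, and nephrolithiasis or severe metabolic acidosis stops topiramate.

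**Conclusion.** The concern holds. Assuming that severe means a GFR below 30 and moderate starts at 30, the exclusion contradicts itself for GFR 30-44, 30-49 or 30-59 mL/min/1.73m², according to the upper limit of moderate, and nothing elsewhere in the document resolves it. Whether the word or the number was intended cannot be determined from the text.

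Severity is low and confidence is medium. The number of patients affected is not given and is probably small at ages 12-24. The sample size, the precision figures for dropout and tolerability, and the analyses are untouched.

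**What to change.** In the Section IV.B exclusion criteria, make the bound match the grades named. Raise it to the upper limit of the moderate band that the sponsor and pharmacy intend, for example GFR below 60 mL/min/1.73m² (an assumed figure, for them to confirm). Use the same bound on the inclusion/exclusion form and when reading the metabolic panel already drawn at screening. Only if they confirm that below 30 was intended, delete the reference to moderate impairment and keep the number.

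The cost is one line in the protocol and the matching line on the form, with no added test. A higher bound may lose a very small number of otherwise eligible patients, with the effect on the recruitment allowance shown in the working; removing the reference to moderate impairment loses none.

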Nausea, Vomiting, Diarrhea	DSMP				
Rare, but Serious ⁴⁰					

Acute myopia, Secondary angle closure glaucoma	DSMP
Oligohidrosis, Hyperthermia	DSMP (including temperature at every study visit)
Metabolic acidosis	Bicarbonate at enrollment, visit 2, and visit 4
Suicidal ideation/attempt	DSMP with assessment at every study visit
Fetal toxicity	Pregnancy tests at enrollment and every study visit
(Pregnancy Risk Factor Category D- positive evidence of risk)	Requirement for females to either have a LARC (majority) or documented commitment to use 2 forms of birth control
Withdrawal symptoms	Gradual discontinuation at the end of the study
Hyperammonemia and encephalopathy	Drug interaction check; DSMP
Kidney stones	BMP at enrollment, visit 2, and visit 4; Drug interaction check; DSMP
Topiramate-Ethanol interaction (potential to cause increased CNS depression)	Counseling about alcohol avoidance, and specific language about this risk in the consent/assent

Methods for systematically assessing changes in mood, suicidality, and cognition.

Mood:

Changes in mood will be systematically screened for using the Center for Epidemiologic Studies Depression Scale (CES-D). This is a 20-item self-report questionnaire that covers areas including depressed mood, feelings of guilt/worthlessness, helplessness, psychomotor retardation, loss of appetite and sleep disturbance over the previous week. ⁴⁶ This instrument has yielded adequate internal reliability that is robust to age, clinical vs. nonclinical setting, and risk of bias. ⁴⁷ The original version of the measure is appropriate for individuals 12 years of age and older. The CES-D is routinely administered to individuals receiving care at the Children's Colorado Bariatric Surgery Center at every follow-up pre-operative and post-operative clinic appointment.

The proposed study will additionally administer the CES-D at all study visits not aligned with a clinical visit and will be scored by the PI or professional research assistant. A CES-D score <20 indicates no to mild depressive symptoms. And a CES-D score ≥20 indicates elevated depressive symptoms. This is based on a metaregression that supported higher cut points having better diagnostic accuracy.⁴⁷

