- **5. Will any formal interim analysis be performed?:** Interim assessments of feasibility, acceptability, and safety per above will be performed, but there will be no formal interim analysis for this 12-month study.
- **6. Are there defined** participant **discontinuation criteria?**: There are no *participant* discontinuation criteria. However, there are defined *drug* discontinuation criteria as follows:
 - a) Development of an anaphylactic allergic reaction, pulmonary hypertension, evidence of new valvular heart disease, uncontrolled systemic hypertension, new arrhythmia (including persistent tachycardia), severe anxiety unresponsive to dose decrease, psychiatric disorder that cannot be adequately treated with psycho- and/or pharmacotherapy at the discretion of the study's clinical psychologist, serotonin syndrome, or pregnancy during the pharmacotherapy intervention will lead to discontinuation of phentermine.
 - b) Development of an anaphylactic allergic reaction, nephrolithiasis, severe, persistent cognitive difficulties, psychiatric disorder that cannot be adequately treated with psychoand/or pharmacotherapy at the discretion of the study's clinical psychologist, new acute myopia or secondary angle closure glaucoma, severe metabolic acidosis, hyperammonemia with encephalopathy, or pregnancy during the pharmacotherapy intervention will lead to discontinuation of topiramate.
 - c) If one medication is stopped secondary to the criteria above, the participant, if in agreement, will be continued on the other medication as monotherapy.
 - d) With consent, participants for whom one or both medications are stopped will continue to be followed according to the proposed study timeline.

7. How will the PI/research team determine if an adverse event (AE) is related to either of the study drugs?

Relatedness will be defined according to the National Institutes of Health National Institute on Aging Data Safety and Monitoring Plan Toolkit template (https://www.nia.nih.gov/research/dgcg/clinical-research-study-investigators-toolbox/data-and-safety-monitoring) as follows:

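### The fixed end-of-study topiramate step-down does not fit participants held at 50 mg or 25 mg under the protocol's own highest-tolerated-dose footnote

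*Combined protocol and SAP*

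**What the plan says.** Section IV.C raises topiramate by 25 mg a week. It starts with "Week 1: 4mg phentermine + 25mg immediate release topiramate", continues with "Week 2: 8mg phentermine + 50mg immediate release topiramate" and a third step at 75 mg, and reaches the goal in "Weeks 4-12: 16mg phentermine + 100mg immediate release topiramate". Footnote (*) provides for those who cannot reach the goal: "Participants who do not tolerate goal doses will be maintained at the highest tolerated dose".

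The discontinuation block, which begins at Visit 4, has a single path: "Week 13: Discontinue Phentermine + Decrease topiramate to 50mg", followed by "Week 14: Decrease topiramate to 25mg for 7 days, then discontinue". The paragraph above the schedule explains that the taper is there to avoid discontinuation symptoms.

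Two other places bear on stopping topiramate. In Table 2 the mitigation against withdrawal symptoms is "Gradual discontinuation at the end of the study". In the Data and Safety Monitoring Plan, item 6(b) lists events that "will lead to discontinuation of topiramate"; item 6(d) keeps such participants in follow-up. Neither part of item 6 mentions a taper. The hepatic-impairment footnote in Section IV.C refers to a separately titled procedure on reducing or discontinuing study drug, but no section with that title appears in the text available for review.

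**The concern.** The step-down is written in absolute milligrams that suit someone on the goal dose, while the footnote to the same schedule allows participants to be below it. The plan expects lower doses in several places. Besides footnote (*), the hepatic-impairment footnote allows reduction for side effects, the mood section lists a reduction of study medication as a possible response, and the cognition section treats severe cognitive difficulty as a ground for reduction or discontinuation. The participants for whom the step-down may not work are therefore those who have already had side effects.

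Contact is also sparse at this stage. Visit 4 is the last study visit in Table 3. The next standard call, Phone Call 8, comes one week after the last dose. No standard contact is scheduled during weeks 13 and 14, when an unclear instruction would have to be interpreted. Participants may call the principal investigator about symptoms. Extra weekly calls are promised for additional dose titration, but the text does not say whether the step-down counts as such.

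**Working it through.** The plan states no statistical figure on this point, so there is none to reproduce. The check sets the discontinuation lines against each dose that the footnote permits.

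**Inputs.** Titration steps, footnote (*), and the week 13 and 14 amounts come from Section IV.C. The assumption is that a participant held below goal is held at one of the listed steps. As a check on the steps, 25 mg × week number gives 25, 50, 75 and 100 mg for weeks 1 to 4, which matches the schedule.

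**Formula.** Week 13 change = 50 mg − held dose; relative change = 50 / held dose − 1.

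| Held dose | Week 13 change | Relative change | Amounts if applied as stated |
|---|---|---|---|
| 100 mg | 50 − 100 = −50 mg | −50% | 100, 50, 25, stop |
| 75 mg | 50 − 75 = −25 mg | −33% | 75, 50, 25, stop |
| 50 mg | 50 − 50 = 0 mg | 0% | 50, 50, 25, stop |
| 25 mg | 50 − 25 = +25 mg | +100% | 25, 50, 25, stop |

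The block is a decrease in both weeks from 100 and 75 mg. From 50 mg the week 13 line is not a decrease, but the sequence as a whole is still gradual. From 25 mg the word *decrease* and the amount 50 mg cannot both be followed, and 50 mg is the step above the highest dose tolerated.

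**Timing of contact.** Visits 2, 3 and 4 are each four weeks after the previous visit, so Visit 4 falls 4 + 4 + 4 = 12 weeks after Visit 1. The step-down takes 2 weeks and Phone Call 8 follows 1 week after the last dose. That leaves about 2 + 1 = 3 weeks between Visit 4 and the next standard contact.

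**Early stopping.** Section IV.F plans on 85% not discontinuing medication for adverse effects, so 15% do. Assuming that rate holds in the active arm:

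- 7 active participants: expected 0.15 × 7 = 1.05; chance of at least one = 1 − 0.85^7 = 68%.
- 5 active participants (the minimum): expected 0.15 × 5 = 0.75; chance of at least one = 1 − 0.85^5 = 56%.

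The 15% covers stopping study medication in general, and under item 6(c) someone who stops only phentermine may continue topiramate. These figures indicate only that early stopping is plausible in a trial of this size. They do not size the group held at 25 mg, for which the documents give no rate.

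**The case against.** A reader might infer that the protocol orders a dose increase for a participant on 25 mg. It does not. The line says *decrease*, and the footnote holds such a participant at the highest tolerated dose. The supportable statement is that the line cannot be carried out as written. Exposure to an untolerated dose would arise only if someone applied the stated amount regardless. An instruction that cannot be followed still needs repair.

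A reader might also infer that early stoppers have no step-down at all. That goes beyond the evidence. Item 6(b) is silent rather than contradictory: Table 2 ties gradual withdrawal to the end of the study, and nothing says it should extend to event-driven stopping such as anaphylaxis or severe metabolic acidosis. Whether it should is a clinical matter. The procedure cited in Section IV.C may settle it, and the Safety Officer approves criteria for modifying or discontinuing study drugs. What stands is that the available text does not answer the question.

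Nor is an effect on the primary aim established. Section IV.F defines the tolerability rate by discontinuation for adverse effects, and the Study Med Form is collected at Visits 2 to 4. An event in weeks 13 or 14 could be recorded at Phone Call 8 but would not ordinarily change that rate.

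**Conclusion.** The point holds as an internal inconsistency in the dosing text. The discontinuation block fits two of the four doses a participant may hold (100 and 75 mg). At 50 mg the mismatch is one of wording, because the sequence remains gradual. At 25 mg the block conflicts with footnote (*): the stated amount exceeds the highest tolerated dose by 25 mg. This rests on holding at the listed steps; the number affected is unknown.

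The early-stopping part is narrower. The available text does not say whether the withdrawal mitigation applies under item 6(b), and the procedure that might say so cannot be checked. The matter is relevant to safety, in participants as young as 12. It does not affect the sample size or the planned analyses.

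**What to change.** Reconcile the discontinuation block with footnote (*) so that the text covers every topiramate dose at which a participant may be held at Visit 4. Include or locate the cited dose reduction and discontinuation procedure, and align it with the withdrawal-symptom row of Table 2 and item 6(b), so that the protocol states whether the mitigation applies when topiramate is stopped early. The study physicians and pharmacy should set the actual steps; no dose or stopping rule is proposed here.

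The cost is a wording amendment. Dispensing for weeks 13 and 14 may need to depend on the dose held, arranged with matching placebo so that the blind is kept. No visits or participants are added.
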